7.8. Appendix 8 Clinically Relevant Complication AE terms

Asthma & COPD & bronchial hyperreactivity (Preferred terms)
Acute post asthmatic amyotrophy
Asthma late onset
Obstructive airways disorder
Asthma
Bronchospasm
Asthma exercise induced
Status asthmaticus
Asthma-chronic obstructive pulmonary disease overlap syndrome
Asthmatic crisis
Wheezing
Bronchial hyperreactivity
Bronchial obstruction
Bronchostenosis
Obliterative bronchiolitis
Bronchiolitis obliterans syndrome
Bronchitis chronic
Childhood asthma
Chronic obstructive pulmonary disease
Cough variant asthma
Infective exacerbation of chronic obstructive airways disease
Occupational asthma
Reactive airways dysfunction syndrome
Reversible airways obstruction
Unilateral bronchospasm
Asthma
Bronchitis chronic
Obstructive airways disorder

Respiratory Distress (Preferred Terms)
Respiratory Distress

Bronchitis (Preferred Terms)
Bronchitis
Bronchitis bacterial
Tracheobronchitis
Bronchitis viral
Allergic bronchitis
Pertussis
Bronchitis chemical
Bronchitis fungal
Bronchitis haemophilus
Bronchitis moraxella
Bronchitis mycoplasmal
Bronchitis pneumococcal
Coxsackie bronchitis
Fibrinous bronchitis
Enterobacter tracheobronchitis
Eosinophilic bronchitis
Herpes simplex bronchitis
Tracheobronchitis mycoplasmal
Noninfective bronchitis
Parainfluenzae viral bronchitis
Parainfluenzae viral laryngotracheobronchitis
Pseudomonas bronchitis
Respiratory syncytial virus bronchitis
Sinobronchitis

Bronchitis (Preferred Terms)
Streptococcal bronchitis
Tracheobronchitis bacterial
Tracheobronchitis viral
CHF Exacerbation (Preferred Term)
Cardiac failure congestive
Cardiac Arrhythmia (Preferred Terms)
Chronotropic incompetence
Bezold-Jarisch reflex
Cardiac arrest
Cardiac death
Cardiac telemetry abnormal
Cardio-respiratory arrest
Electrocardiogram abnormal
Electrocardiogram ambulatory abnormal
Heart rate abnormal
Palpitations
Respiratory sinus arrhythmia magnitude abnormal
Respiratory sinus arrhythmia magnitude decreased
Respiratory sinus arrhythmia magnitude increased
Bradycardia
Ventricular asystole
Accessory cardiac pathway
Adams-Stokes syndrome
Agonal rhythm
Atrial conduction time prolongation
Atrioventricular block
Atrioventricular block complete
Atrioventricular block first degree
Atrioventricular block second degree
Atrioventricular conduction time shortened
Atrioventricular dissociation
Atrioventricular node dysfunction
Bifascicular block
BRASH syndrome
Brugada syndrome
Bundle branch block
Bundle branch block bilateral
Bundle branch block left
Bundle branch block right
Conduction disorder
Defect conduction intraventricular
Electrocardiogram delta waves abnormal
Lenegre's disease
Long QT syndrome
Paroxysmal atrioventricular block
Sinoatrial block
Trifascicular block
Ventricular dyssynchrony
Wolff-Parkinson-White syndrome
Nodal arrhythmia
Sinus arrest
Sinus arrhythmia
Arrhythmia
Heart rate irregular

Cardiac Arrhythmia (Preferred Terms)
Holiday heart syndrome
Pacemaker generated arrhythmia
Pacemaker syndrome
Paroxysmal arrhythmia
Reperfusion arrhythmia
Withdrawal arrhythmia
Atrial fibrillation
Atrial flutter
Atrial parasystole
Congenital supraventricular tachycardia
Frederick's syndrome
Junctional ectopic tachycardia
Supraventricular extrasystoles
Supraventricular tachyarrhythmia
Anomalous atrioventricular excitation
Cardiac fibrillation
Cardiac flutter
Extrasystoles
Tachyarrhythmia
Cardiac fibrillation
Parasystole
Rhythm idioventricular
Ventricular arrhythmia
Ventricular extrasystoles
Ventricular fibrillation
Ventricular flutter
Ventricular parasystole
Ventricular pre-excitation
Andersen-Tawil syndrome
Arrhythmia neonatal
Arrhythmogenic right ventricular dysplasia
Atrioventricular node dispersion
Brugada syndrome
Foetal arrhythmia
Foetal heart rate disorder
Foetal tachyarrhythmia
Heart block congenital
Junctional ectopic tachycardia
Long QT syndrome congenital
Lown-Ganong-Levine syndrome
Neonatal bradyarrhythmia
Neonatal tachyarrhythmia
Wolff-Parkinson-White syndrome congenital
Baseline foetal heart rate variability disorder
Cardiac arrest neonatal
Cardio-respiratory arrest neonatal
Foetal cardiac arrest
Foetal heart rate acceleration abnormality
Foetal heart rate deceleration abnormality

Renal Impairment (Preferred Terms)
Atypical haemolytic uraemic syndrome
Anuria
Renal failure
Cardiorenal syndrome

Chronic kidney disease
End stage renal disease
Renal impairment
Crush syndrome
Diabetic end stage renal disease
Hepatorenal failure
Foetal renal impairment
Prerenal failure
Haemolytic uraemic syndrome
Hepatorenal syndrome
Nail-patella syndrome
Renal injury
Neonatal anuria
Pancreatorenal syndrome
Postoperative renal failure
Postrenal failure
Renal failure neonatal
Renal impairment neonatal
Scleroderma renal crisis
Subacute kidney injury

X-ray or Radiologic Pneumonia (Preferred Terms)
Eosinophilic pneumonia
Eosinophilic pneumonia acute
Eosinophilic pneumonia chronic
Pneumonitis
Pneumonitis chemical
Idiopathic interstitial pneumonia
Pneumonia
Atypical pneumonia
COVID-19 pneumonia
Embolic pneumonia
Enterobacter pneumonia
Haemorrhagic pneumonia
Miliary pneumonia
Paraneoplastic pneumonia
Pneumocystis jirovecii pneumonia
Pneumonia
Pneumonia acinetobacter
Pneumonia adenoviral
Pneumonia anthrax
Pneumonia bacterial
Pneumonia blastomyces
Pneumonia bordetella
Pneumonia chlamydial
Pneumonia cryptococcal
Pneumonia cytomegaloviral
Pneumonia escherichia
Pneumonia fungal
Pneumonia haemophilus
Pneumonia helminthic
Pneumonia herpes viral
Pneumonia influenzal
Pneumonia klebsiella
Pneumonia legionella
Pneumonia measles
Pneumonia moraxella
Pneumonia mycoplasmal
Pneumonia necrotising

Pneumonia parainfluenzae viral
Pneumonia pneumococcal
Pneumonia proteus
Pneumonia pseudomonal
Pneumonia respiratory syncytial viral
Pneumonia salmonella
Pneumonia serratia
Pneumonia staphylococcal
Pneumonia streptococcal
Pneumonia toxoplasmal
Pneumonia tularaemia
Pneumonia viral
Pneumonic plague
Post procedural pneumonia
Pulmonary mucormycosis
Pulmonary nocardiosis
Pulmonary paracoccidioidomycosis
Pulmonary sepsis
Pulmonary sporotrichosis
Pulmonary syphilis
Pulmonary trichosporonosis
Pulmonary tuberculosis
Pneumococcal infection
Pneumovirus test positive
Pulmonary tuberculoma

Respiratory Arrest or Failure (Preferred Terms)

Acute respiratory distress syndrome
Acute respiratory failure
Agonal respiration
Apnoea
Apnoeic attack
Bradypnoea
Cardio-respiratory distress
Central-alveolar hypoventilation
Chronic respiratory failure
Hypopnoea
Hypoventilation
Hypoventilation neonatal
Infantile apnoea
Lung hypoinflation
Neonatal respiratory arrest
Neonatal respiratory depression
Neonatal respiratory distress
Neonatal respiratory distress syndrome
Neonatal respiratory failure
Postoperative respiratory distress
Postoperative respiratory failure
Respiratory arrest
Respiratory depression
Respiratory depth decreased
Respiratory distress
Respiratory failure
Respiratory paralysis
Adaptive servo-ventilation
Alveolar oxygen partial pressure abnormal
Alveolar oxygen partial pressure decreased
Alveolar-arterial oxygen gradient increased

Respiratory Arrest or Failure (Preferred Terms)
Anoxia
Asphyxia
Automatic positive airway pressure
Bilevel positive airway pressure
Blood gases abnormal
Capnogram abnormal
Carbon dioxide abnormal
Carbon dioxide increased
Cardiopulmonary failure
Cardio-respiratory arrest
Cardio-respiratory arrest neonatal
Cheyne-Stokes respiration
Chronic respiratory disease
Continuous positive airway pressure
Cyanosis central
Dependence on oxygen therapy
Dependence on respirator
Dyspnoea at rest
Endotracheal intubation
End-tidal CO2 abnormal
End-tidal CO2 decreased
Hyperbaric oxygen therapy
Hypercapnia
Hypercapnic coma
Hypoxia
Intermittent positive pressure breathing
Irregular breathing
Life support
Lung assist device therapy
Mechanical ventilation
Mechanical ventilation complication
Neonatal anoxia
Neonatal asphyxia
Neonatal hypoxia
Neonatal respiratory acidosis
Neonatal respiratory distress syndrome prophylaxis
Neonatal tachypnoea
Oxygen saturation abnormal
Oxygen saturation decreased
Oxygen therapy
PaO2/FiO2 ratio decreased
PCO2 abnormal
PCO2 decreased
PCO2 increased
PO2 abnormal
PO2 decreased
Positive end-expiratory pressure
Positive expiratory pressure therapy
Respiration abnormal
Respiratory acidosis
Respiratory disorder
Respiratory disorder neonatal
Respiratory fatigue
Respiratory gas exchange disorder
Use of accessory respiratory muscles
Venous oxygen partial pressure abnormal

Respiratory Arrest or Failure (Preferred Terms)
Venous oxygen partial pressure decreased
Venous oxygen saturation abnormal
Venous oxygen saturation decreased
Ventilation perfusion mismatch
Ventilation/perfusion scan abnormal
Wean from ventilator
Weaning failure
Acute respiratory failure
Agonal respiration
Apnoea
Apnoeic attack
Bradypnoea
Central-alveolar hypoventilation
Hypopnoea
Hypoventilation
Hypoventilation neonatal
Infantile apnoea
Lung hypoinflation
Neonatal respiratory arrest
Neonatal respiratory depression
Neonatal respiratory failure
Postoperative respiratory failure
Respiratory arrest
Respiratory depression
Respiratory depth decreased
Respiratory failure
Respiratory paralysis
Adaptive servo-ventilation
Alveolar oxygen partial pressure abnormal
Alveolar oxygen partial pressure decreased
Anoxia
Apnoea test abnormal
Asphyxia
Automatic positive airway pressure
Bilevel positive airway pressure
Blood gases abnormal
Capnogram abnormal
Carbon dioxide abnormal
Carbon dioxide increased
Cardiopulmonary failure
Cardio-respiratory arrest
Cardio-respiratory arrest neonatal
Cardio-respiratory distress
Cheyne-Stokes respiration
Continuous positive airway pressure
Cyanosis
Cyanosis central
Dependence on oxygen therapy
Dependence on respirator
Dyspnoea
End-tidal CO2 abnormal
End-tidal CO2 decreased
Hyperbaric oxygen therapy
Hypercapnia
Hypercapnic coma
Hypoxia

Respiratory Arrest or Failure (Preferred Terms)
Intermittent positive pressure breathing
Irregular breathing
Life support
Lung assist device therapy
Mechanical ventilation
Mechanical ventilation complication
Neonatal anoxia
Neonatal asphyxia
Neonatal dyspnoea
Neonatal hypoxia
Neonatal respiratory acidosis
Neonatal respiratory distress syndrome prophylaxis
Oxygen saturation abnormal
Oxygen saturation decreased
Oxygen therapy
PaO2/FiO2 ratio decreased
PCO2 abnormal
PCO2 increased
PO2 abnormal
PO2 decreased
Positive end-expiratory pressure
Respiration abnormal
Respiratory acidosis
Respiratory disorder
Respiratory disorder neonatal
Respiratory distress
Respiratory gas exchange disorder
Venous oxygen partial pressure abnormal
Venous oxygen partial pressure decreased
Venous oxygen saturation abnormal
Venous oxygen saturation decreased
Ventilation perfusion mismatch
Ventilation/perfusion scan abnormal
Wean from ventilator
Weaning failure

Pulmonary Embolism (Preferred Terms)
Pulmonary embolism
Pulmonary infarction
Post procedural pulmonary embolism
Pulmonary artery thrombosis
Pulmonary microemboli
Pulmonary oil microembolism
Pulmonary thrombosis
Pulmonary tumour thrombotic microangiopathy
Pulmonary venous thrombosis
Septic pulmonary embolism

Pleural Effusion (Preferred Terms)
Pleural effusion
Haemothorax
Eosinophilic pleural effusion
Traumatic haemothorax
Hepatic hydrothorax
Hydrothorax

Procedural pneumothorax
Neonatal pneumothorax
Paraneoplastic pleural effusion
Pleuroperitoneal communication
Atelectasis (Preferred Terms)
Atelectasis
Atelectasis neonatal

Acute Coronary Events (Preferred Terms)
Acute myocardial infarction
Acute coronary syndrome
Myocardial ischaemia
Myocardial infarction
Coronary artery dissection
Coronary artery aneurysm
Angina pectoris
Angina unstable
Prinzmetal angina
Anginal equivalent
Congenital coronary artery malformation
Coronary artery insufficiency
Arteriosclerosis coronary artery
Arteriospasm coronary
Arteritis coronary
Coronary artery disease
Cardiac perfusion defect
Microvascular coronary artery disease
Chronic coronary syndrome
Coronary artery stenosis
Haemorrhage coronary artery
Coronary artery compression
Coronary artery dilatation
Coronary artery embolism
Coronary artery occlusion
Coronary artery perforation
Coronary artery reocclusion
Coronary artery restenosis
Coronary artery thrombosis
Coronary bypass stenosis
Coronary bypass thrombosis
Coronary no-reflow phenomenon
Coronary ostial stenosis
Coronary sinus dilatation
Coronary steal syndrome
Coronary vascular graft occlusion
Coronary vascular graft stenosis
Diabetic coronary microangiopathy
Subendocardial ischaemia
Papillary muscle infarction
Kounis syndrome
Myocardial reperfusion injury
Myocardial stunning
Periprocedural myocardial infarction
Post procedural myocardial infarction
Postinfarction angina
Silent myocardial infarction
Subclavian coronary steal syndrome
Wellens' syndrome
Altered Mental Status (SOC)
Psychiatric disorders
Acute Cerebrovascular Events (Preferred Terms)
Cerebrovascular accident
Subdural haematoma

Acute Cerebrovascular Events (Preferred Terms)
Superior sagittal sinus thrombosis
Cerebrovascular disorder
Spinal artery embolism
Amaurosis fugax
Amyloid related imaging abnormalities
Amyloid related imaging abnormality-oedema/effusion
Amyloid related imaging abnormality-microhaemorrhages and haemosiderin deposits
Intracranial aneurysm
Brain hypoxia
Cerebral artery embolism
Cerebral artery occlusion
Cerebral artery perforation
Cerebral artery stenosis
Cerebral artery thrombosis
Aseptic cavernous sinus thrombosis
Cerebral infarction
Haemorrhagic transformation stroke
Subarachnoid haemorrhage
Cerebral arteriosclerosis
Basal ganglia haemorrhage
Basal ganglia haematoma
Basal ganglia infarction
Basal ganglia stroke
Basilar artery aneurysm
Basilar artery occlusion
Basilar artery perforation
Basilar artery stenosis
Vertebrobasilar insufficiency
Basilar artery thrombosis
Benedikt's syndrome
Reversible cerebral vasoconstriction syndrome
Vascular encephalopathy
Haemorrhage intracranial
Blood brain barrier defect
Cerebral congestion
Brain stem haemorrhage
Brain stem embolism
Brain stem haematoma
Brain stem infarction
Brain stem ischaemia
Brain stem microhaemorrhage
Brain stem stroke
Brain stem thrombosis
Capsular warning syndrome
Embolic stroke
Carotid aneurysm rupture
Carotid arterial embolus
Carotid arteriosclerosis
Carotid artery aneurysm
Carotid artery disease
Carotid artery dissection
Carotid artery dolichoectasia
Carotid artery insufficiency
Carotid artery occlusion
Carotid artery perforation
Carotid artery restenosis

Acute Cerebrovascular Events (Preferred Terms)
Carotid artery stenosis
Carotid artery thrombosis
Cavernous sinus thrombosis
Central nervous system haemorrhage
Central nervous system vasculitis
Cerebellar artery occlusion
Cerebellar artery thrombosis
Cerebellar atherosclerosis
Cerebellar haemorrhage
Cerebellar embolism
Cerebellar haematoma
Cerebellar infarction
Cerebellar ischaemia
Cerebellar microhaemorrhage
Cerebellar stroke
Cerebral amyloid angiopathy
Cerebral aneurysm perforation
Cerebral aneurysm ruptured syphilitic
Cerebral vasoconstriction
Cerebral arteriovenous malformation haemorrhagic
Cerebral arteritis
Intraoperative cerebral artery occlusion
Cerebral artery restenosis
Cerebral haemorrhage
Cerebral capillary telangiectasia
Cerebral circulatory failure
Cerebral gas embolism
Cerebral haematoma
Cerebral haemorrhage foetal
Cerebral haemorrhage neonatal
Traumatic intracranial haemorrhage
Cerebral hemosiderin deposition
Cerebral hyperperfusion syndrome
Cerebral hypoperfusion
Cerebral infarction foetal
Cerebral ischaemia
Cerebral microangiopathy
Cerebral microhaemorrhage
Cerebral microembolism
Cerebral microinfarction
Cerebral reperfusion injury
Cerebral septic infarct
Cerebral small vessel ischaemic disease
Cerebral thrombosis
Cerebral vascular occlusion
Cerebral vasodilatation
Cerebral venous sinus thrombosis
Cerebral venous thrombosis
Cerebrovascular arteriovenous malformation
Foetal cerebrovascular disorder
Cerebrovascular insufficiency
Cerebrovascular pseudoaneurysm
Cerebrovascular stenosis
Charcot-Bouchard microaneurysms
Chronic cerebrospinal venous insufficiency

Acute Cerebrovascular Events (Preferred Terms)
Claude's syndrome
Spinal vessel congenital anomaly
Giant cell arteritis
Delayed ischaemic neurological deficit
Dural arteriovenous fistula
Embolitic cerebellar infarction
Embolitic cerebral infarction
Epidural haemorrhage
Extradural haematoma
Jugular vein haemorrhage
Extra-axial haemorrhage
Extracerebral cerebral haematoma
Haemorrhagic stroke
Intraventricular haemorrhage neonatal
Spinal cord haemorrhage
Subdural haemorrhage
Haemorrhagic cerebral infarction
Hypertensive cerebrovascular disease
Inner ear infarction
Transient ischaemic attack
Internal capsule infarction
Internal carotid artery deformity
Intracranial artery dissection
Intracranial haematoma
Ruptured cerebral aneurysm
Intracranial tumour haemorrhage
Intraventricular haemorrhage
Ischaemic cerebral infarction
Ischaemic stroke
Lacunar infarction
Lacunar stroke
Lateral medullary syndrome
Lenticulostriatal vasculopathy
Meningorrhagia
Migrainous infarction
Moyamoya disease
Pituitary infarction
Subarachnoid haemorrhage neonatal
Subdural haemorrhage neonatal
Precerebral artery occlusion
Vertebral artery occlusion
Perinatal stroke
Periventricular haemorrhage neonatal
PHACES syndrome
Pituitary apoplexy
Pituitary haemorrhage
Post cardiac arrest syndrome
Post procedural stroke
Post stroke depression
Precerebral arteriosclerosis
Precerebral artery embolism
Precerebral artery thrombosis
Pseudostroke
Putamen haemorrhage
Susac's syndrome
Reversible ischaemic neurological deficit

Acute Cerebrovascular Events (Preferred Terms)
Sneddon's syndrome
Spinal artery thrombosis
Spinal cord haematoma
Spinal cord infarction
Spinal epidural haemorrhage
Spinal epidural haematoma
Spinal stroke
Spinal subarachnoid haemorrhage
Spinal subdural haemorrhage
Spinal subdural haematoma
Spinal vascular disorder
Spontaneous internal carotid artery recanalisation
Stroke in evolution
Subarachnoid haematoma
Subclavian steal syndrome
Superficial siderosis of central nervous system
Weber's syndrome
Thalamic infarction
Thalamus haemorrhage
Thrombotic cerebral infarction
Thrombotic stroke
Transient aphasia
Transverse sinus stenosis
Transverse sinus thrombosis
Traumatic intracranial haematoma
Vascular cognitive impairment
Vein of Galen aneurysmal malformation
Vertebral artery aneurysm
Vertebral artery arteriosclerosis
Vertebral artery dissection
Vertebral artery perforation
Vertebral artery stenosis
Vertebral artery thrombosis
Vertebrobasilar dolichoectasia
Vertebrobasilar stroke
Wyburn Mason's syndrome

Seizure (Preferred Terms)
Acquired epileptic aphasia
Atonic seizures
Atypical benign partial epilepsy
Automatism epileptic
Autonomic seizure
Baltic myoclonic epilepsy
Benign rolandic epilepsy
Change in seizure presentation
Clonic convulsion
Congenital bilateral perisylvian syndrome
Convulsion in childhood
Convulsions local
Convulsive threshold lowered
Dreamy state
Early infantile epileptic encephalopathy with burst-suppression
Epilepsy
Epilepsy surgery
Epilepsy with myoclonic-atonic seizures

Seizure (Preferred Terms)
Epileptic aura
Epileptic psychosis
Faciobrachial dystonic seizure
Febrile convulsion
Febrile infection-related epilepsy syndrome
Focal dyscognitive seizures
Frontal lobe epilepsy
Gelastic seizure
Generalised onset non-motor seizure
Generalised tonic-clonic seizure
Hemiconvulsion-hemiplegia-epilepsy syndrome
Hemimegalencephaly
Hyperglycaemic seizure
Hypocalcaemic seizure
Hypoglycaemic seizure
Hyponatraemic seizure
Idiopathic generalised epilepsy
Infantile spasms
Jeavons syndrome
Juvenile absence epilepsy
Juvenile myoclonic epilepsy
Lafora's myoclonic epilepsy
Lennox-Gastaut syndrome
Migraine-triggered seizure
Myoclonic epilepsy
Myoclonic epilepsy and ragged-red fibres
Neonatal epileptic seizure
Neonatal seizure
Parietal lobe epilepsy
Partial seizures
Partial seizures with secondary generalisation
Petit mal epilepsy
Polymicrogyria
Post stroke epilepsy
Post stroke seizure
Postictal headache
Postictal paralysis
Postictal psychosis
Postictal state
Seizure
Seizure anoxic
Seizure cluster
Seizure like phenomena
Severe myoclonic epilepsy of infancy
Simple partial seizures
Status epilepticus
Sudden unexplained death in epilepsy
Temporal lobe epilepsy
Tonic clonic movements
Tonic convulsion
Tonic posturing
Topectomy
Transient epileptic amnesia
Aura
Drop attacks
Narcolepsy
Preictal state
Seizure prophylaxis
Tongue biting
Altered state of consciousness

Seizure (Preferred Terms)
Depressed level of consciousness
Loss of consciousness
Clonus
Hypotonia
Syncope (Preferred Terms)
Syncope
Systemic Inflammatory Response (Preferred Terms)
Systemic inflammatory response syndrome
New Neurological Deficit (SOC)
Nervous system disorders
Asthenia (Preferred Terms)
Asthenia
Cachexia
Cancer fatigue
Fatigue
Chronic fatigue syndrome
Decreased activity
Malaise
Lethargy
Listless
Sluggishness
Dehydration (Preferred Terms)
Dehydration
Dry eye
Dry mouth
Dry skin
Dry throat
Fluid balance negative
Lip dry
Mucosal dryness
Nasal dryness
Tongue dry
Metabolic Disturbances (SOC)
Metabolism and nutrition disorders

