8.2.3. Predefined Clinically Relevant Disease Associated with RT-PCR-confirmed RSV-mediated ARI

A participant will be considered to have clinically relevant disease with specific parameters associated with an RT-PCR-confirmed RSV-mediated ARI if the following criteria are met:

- The participant has an RT-PCR-confirmed RSV-mediated ARI as defined in Section [8.2.2](#)
- Any of the following is associated with the ARI:

Hospitalization

Emergency department visit

Per clinical judgement, at least one of the following complications: asthma exacerbation, COPD exacerbation, respiratory distress, bronchitis, bronchial hyperreactivity, CHF exacerbation, cardiac arrhythmia, renal impairment or the presence of X-ray or radiological confirmed pneumonia, respiratory arrest and/or failure, pulmonary embolism, pleural effusion, atelectasis, acute coronary events, acute cerebrovascular events, altered mental status, seizure, syncope, systemic inflammatory response syndrome (SIRS), new neurological deficit, asthenia, dehydration or metabolic disturbances

For measurements at the site, decreased oxygen saturation is defined as oxygen saturation of <92% for participants with a baseline oxygen saturation of $\geq 92\%$ at randomization; for participants with baseline oxygen saturation <92%, decreased oxygen saturation is

defined as a $\geq 3\%$ decrease in their oxygen saturation from baseline^a.

Decreased oxygen saturation based on measurements during medically-attended ARI (ie, hospitalization) is defined as oxygen saturation of $< 92\%$ supporting LRTD.

Tachypnea (at least emerging Grade 2, see [Appendix 4: Toxicity Grading Scale](#))

Need of supplemental oxygen

Hypotension (emerging Grade 3, see [Appendix 4: Toxicity Grading Scale](#))

Pulmonary function test results supporting diagnosis of LRTD

Arterial blood gas results supporting diagnosis of LRTD

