7.14.	Appendix 14 List of preferred terms for VTE (broad)	89
8.	REFERENCES	92

LIST OF IN-TEXT TABLES AND FIGURES

TABLES

Table 1: SAP Version History Summary 5

Table 2: Study Design 8

Table 3: Analysis Sets 9

Table 4: Phase Definitions 13

Table 5: Interval Definition for potential AESI analysis 14

Table 6: Immunogenicity timepoints 15

Table 7: Immunogenicity timepoints during an ARI 16

Table 8: Adjudicator's choices and selection for the primary endpoint 20

Table 9: Alpha spending at the Prespecified Analysis Timepoints 21

Table 10: Secondary Endpoints: Overview of the Testing Order, Timing of the Testing in the Testing Strategy and the Corresponding Alpha 26

Table 11: Example for 'Return to Usual Health' question 35

Table 12: Case Definitions 50

Table 13: Grades for erythema and swelling based on diameter 51

Table 14: Grades for pyrexia based on temperatures 52

Table 15: Adverse Events of (clinical) interest 52

Table 16: Demographic Variables 56

FIGURES

Figure 1: Interim and Primary Analysis Plan 11

AMENDMENT HISTORY**Table 1: SAP Version History Summary**

SAP Version	Approval Date	Change	Rationale
1.0	6 July 2021	Not Applicable	Initial release
2.0	19 November 2021	The amendment is made to align with changes in the Protocol amendment 3	Amendment of the CTP
3.0	23 September 2022	
The amendment of the SAP is made to align with the protocol amendment 4. Additionally, the following were added:
 
 • Clarification on the way potential AESI will be analyzed. • Clarification on the primary analysis definition and the options provided to the Clinical Evaluation Committee • Clarification on the timing of the end-of-study analysis and the population used • Clarification on how to handle missing RSV ARI end dates close to the database lock. • The method used for local nasal swab testing for China sites. • New exploratory endpoints related to clinically relevant diseases and EQ-5D 
Moreover:
 
 • appendix 8 was updated, where AE terms were removed • three ATC terms were added in appendix 10 	Amendment of the CTP

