6.4.1.1.2. Predefined Clinically Relevant Disease Associated with RT-PCR-confirmed RSV-mediated ARI

A participant will be considered to have clinically relevant disease with specific parameters associated with an RT-PCR-confirmed RSV-mediated ARI if the following criteria are met:

The participant has an RT-PCR-confirmed RSV-mediated ARI as defined in Section 6.4.1.1.1.

Any of the following is associated with the ARI:

- **Hospitalization** (as collected on eCRF AE pages (linked via acute respiratory infection form or complications linked to ARI form), medical encounters [Intensive Care Unit and Hospital inpatient department] form and MRU pages [Emerging Hospitalization admissions (Emerging emergency department visits are not taken into account)])
- **Emergency department visit** (as assessed on the eCRF medical encounters form and MRU pages [emerging MRU to be summarized])
- At least one of the following **complications**: asthma, COPD, respiratory distress, bronchitis, bronchial hyperreactivity, CHF, cardiac arrhythmia, renal impairment or the presence of X-ray or radiological confirmed , respiratory arrest and/or failure, pulmonary embolism, pleural effusion, atelectasis, acute coronary events, acute cerebrovascular events, altered mental status, seizure, syncope, systemic inflammatory response syndrome (SIRS), new neurological deficit, asthenia, dehydration or metabolic disturbances.

See Section 7.8 for the complication terms. These terms will be reported in the AE or the CE domain.

Asthma and chronic obstructive pulmonary disease (COPD) exacerbation supporting LRTD reported in the medically attended ARI form will also be counted, as well as X-ray or radiological confirmed pneumonia from the diagnostic tests form.

- **Decreased oxygen saturation:**
Based on the vital signs form collected at the site: defined as oxygen saturation of <92% for participants with a baseline oxygen saturation of $\geq 92\%$ or missing at randomization; for participants with baseline oxygen saturation <92%, decreased oxygen saturation is defined as a $\geq 3\%$ decrease in their oxygen saturation from baseline
Based on eCRF pages on measurements during a medically attended ARI (eq. hospitalizations): defined as oxygen saturation of <92% supporting LRTD

- **Tachypnea** (at least emerging Grade 2, see respiratory rate at Section 7.6)

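### SAP Appendix 8 lacks acute kidney injury and plain ventricular and supraventricular tachycardia and has a single CHF term, so its complication lists are narrower than the protocol definition behind endpoint #4

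*SAP*

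**What the plan says.** Protocol 8.2.3 introduces the complication component of clinically relevant disease with "Per clinical judgement, at least one of the following complications". The list that follows includes "CHF exacerbation, cardiac arrhythmia, renal impairment".

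SAP 6.4.1.1.2 keeps the composite but drops the reference to clinical judgement and sends the reader to Appendix 8: "See Section 7.8 for the complication terms. These terms will be reported in the AE or the CE domain". It adds form-based routes only for asthma and COPD exacerbation and for radiologically confirmed pneumonia.

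In SAP Appendix 8 (Section 7.8):
- The renal list ends with "Subacute kidney injury".
- The arrhythmia list includes "Congenital supraventricular tachycardia".
- The CHF list consists of "Cardiac failure congestive" alone.

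The SAP version history (Table 1) records for version 3.0 that "appendix 8 was updated, where AE terms were removed". It does not say which terms or why.

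Endpoint #4 is the last confirmatory secondary endpoint, tested hierarchically at 2.5% at study end (SAP 6.4.1.2). Clinically relevant disease stays among the efficacy endpoints of the reduced final analysis (SAP 6.11).

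**The concern.** The term list decides which AE or CE records make an RSV ARI a complication case. A term that is missing from it removes the record, whatever the investigator judged. The pattern of what is in and what is out looks unplanned. The trial enrols adults aged 60 and over, yet foetal, neonatal and congenital variants are listed while the ordinary acute forms of kidney injury and tachycardia are not. Other lists in the same appendix do carry acute terms, such as acute respiratory failure and acute myocardial infarction.

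At stake is agreement between the protocol definition and the programmed definition of a confirmatory endpoint, and possibly some events. The same list feeds the exploratory endpoint of first occurrence of complications (SAP 6.5). Protocol 1.3.2 (footnote l) requires all complications of ARIs to be captured in the eCRF, so the records should exist and the filter would discard them.

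**Working it through.** The plan states no figure on this point, and no power or alpha calculation depends on it. The check is a comparison of texts.

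**Step 1: exact-term search.** The CHF, arrhythmia and renal lists of Appendix 8 were transcribed, with the MedDRA 25.1 additions in Section 7.8.1, and searched without regard to case. That is 1 CHF entry, 98 arrhythmia entries (95 unique; three are printed twice) and 24 renal entries.

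| Term sought | On its list? | Nearest entries present |
|---|---|---|
| Acute kidney injury | No | Subacute kidney injury; also Renal failure, Renal impairment, Prerenal failure, Renal injury, Anuria |
| Ventricular tachycardia | No | Ventricular arrhythmia, Ventricular fibrillation, Ventricular flutter |
| Supraventricular tachycardia | No | The congenital form; also Supraventricular tachyarrhythmia, Tachyarrhythmia |
| Cardiac failure; Cardiac failure acute | No | Cardiac failure congestive |

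**Step 2: other routes inside the appendix.** Section 7.8.1 adds one arrhythmia term (Atrial standstill) and nothing to the renal or CHF lists. Three categories are defined by a whole system organ class: psychiatric, nervous system, and metabolism and nutrition. None of these is renal or cardiac. The absent terms do not appear in the remaining lists.

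**Step 3: other routes inside endpoint #4.** Any one component suffices under SAP 6.4.1.1.2: hospitalization, emergency department visit, decreased oxygen saturation, tachypnea, supplemental oxygen, hypotension, supportive pulmonary function or blood gas results, or another listed complication. An event coded to an absent term is therefore lost to endpoint #4 only if none of these applies to the same ARI.

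**Step 4: the exploratory complications endpoint.** SAP 6.5 uses the same complication list. Hospitalization, oxygen and the other non-complication components do not count there. Only another listed complication in the same ARI would rescue the case.

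**Step 5: size.** Let N be the number of RSV ARIs with one of these complications coded to an absent term. Let f be the share of those that also meet another component or carry a listed term. Then

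loss to endpoint #4 = N × (1 − f).

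The documents give neither N nor f. The loss runs from 0 (f = 1) to N (f = 0), and N itself may be zero.

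**The case against.** The strongest reply is that a case meeting none of the other criteria is a narrow residual. The composite has many routes, and the appendix is broad elsewhere. It lists wheezing, dyspnoea, hypoxia, fatigue and malaise, and it takes in every nervous system and metabolic event. A patient with acute kidney injury or ventricular tachycardia during an RSV ARI will often have been in hospital or have another listed event. General renal and arrhythmia terms are also present. This stands. A reader might infer that all such cases go uncounted, or that the endpoint loses its most important acute events, and the documents support neither.

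A second reply is that the protocol names exacerbation of CHF, not heart failure in general, and the single listed term matches that wording. This also stands. A reader might infer that non-congestive heart failure is a named complication, but it is not. What remains is that a CHF exacerbation coded to a different heart-failure term would be missed.

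Third, which of these phrases are separate preferred terms, and how verbatim reports would code, needs the MedDRA dictionary, which the documents do not contain. The version 3.0 note does not show that these particular terms were removed, or removed by mistake. Both points are correct. They are reasons to ask for reconciliation or an explanation, and they do not close the gap between Protocol 8.2.3 and the list.

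Fourth, the same list applies to both arms, so no bias in VE is shown. That is right; the issue is fidelity to the definition and some precision.

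**Conclusion.** The point holds in this limited form. Appendix 8 is narrower than Protocol 8.2.3 for three complications that the protocol names, and nothing in the SAP explains the difference. Its account of changes to protocol-planned analyses (Section 7.2) does not mention it. Some protocol-named complications would be misclassified. For endpoint #4 this happens only when no other component or listed term applies. For the exploratory complications endpoint it happens unless another listed complication is present. That exploratory endpoint is not among those listed for the reduced final analysis in SAP 6.11, so in the final analysis the point bears mainly on endpoint #4.

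The size is unknown and may be small or zero. A reader might infer a material loss of power; the documents give no term frequencies to support that. The conclusion assumes that the missing phrases are distinct preferred terms in MedDRA 25.1, which must be checked.

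**What to change.** Before the final lock, staff blinded to allocation should compare the renal, arrhythmia and CHF lists with Protocol 8.2.3 in MedDRA 25.1. They should add acute kidney injury, ventricular tachycardia, supraventricular tachycardia and any heart-failure term to which a CHF exacerbation would be coded, or record why a term was deliberately removed in SAP version 3.0. Sinus tachycardia should not be added: it could let a raised heart rate alone qualify, and endpoint #4 does not use tachycardia as a vital-sign criterion.

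Report endpoint #4, and the complications endpoint wherever it is presented, with and without the added terms. State beforehand which version carries the formal test.

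The cost is one term-list edit and one extra sensitivity run. The drawback is timing: the study was terminated on 29 March 2023, so this would be a late change to a confirmatory endpoint. That is why the blinding of those who make it must be documented. SAP version 4.0, which records that termination, itself added terms to Appendix 8, so a change of this kind is feasible.
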